5.8 Statistics

All statistical analysis will be performed using the version of SAS currently used at our institute. All data will be analyzed on the intention to treat basis. All baseline data will be presented using appropriate summarizing statistics. Appropriate comparable statistical analysis will be applied to

- Incidence of new ulcer(s) in treated limb
- Mean time (in days) to healing of incision sites
- Incidence of minor amputations
- Incidence of major amputations

Odds-ratio will be applied to

- The incidence of secondary infection
- Pain in treated limb, associated with tenotomy
- Transfer lesion

Sample-size

The calculation is done with a Type 1 error rate (α) at 5%, and a power (1- β) at 80%. The primary endpoint is number of new ulcers incurred.

In the general diabetic population life time prevalence of diabetic ulcers has been reported at $15-25\%^{24}$, the yearly incidence in the same group is 6%. This study focuses on patients with a deformity reported to have a 1.5 hazard ratio²⁵, and signs of an impending ulcer like callus formation, which has been reported with a relative risk of 11^{26} . The incidence of new diabetic foot ulcers incurred by the study population is set at 10%, according to the above mentioned considerations.

The incidence in the intervention group (μ_A) is set at 6%, so the anticipated reduction in incidence is 4% compared to the incidence in the control group (μ_B) which as above mentioned is set at 10%. However, the numbers for incidence of new diabetic foot ulcers is an uncertain size, especially when looking at the specific group we are looking at, therefore the standard deviation (σ) is set at 10.

The calculator used is a 2 means, 2 sample, 2-sided equality calculator. The formula is

 $nB=(1+1/\kappa) ((\sigma z1-\alpha/2+z1-\beta)/(\mu A-\mu B))2$

nB= Sample size

 κ = The matching ratio

With the above described parameters, the sample size is 98 patients, which due to an expected dropout of 10% will be extended to 110 patients.

6. **Perspective**

The results of these studies will allow us to evaluate if there's a clinical advantage to performing preventive tenotomies. Several studies have shown that tenotomies done by scalpel are safe, and that most patients go on to heal their ulcers, but none have compared tenotomies to standard care, and no studies have looked at tenotomies as a preventive treatment against new ulcers. Our hypothesis is that patients with impending ulcers associated with hammer, mallet and claw toe deformities will have a lower incidence of new ulcers associated with hammer, mallet and claw toe deformities. At the same time, unpublished data from our institute show that tenotomies done by needle has comparable results to tenotomies done by scalpel. The economic perspectives are vast if a preventive minimal invasive procedure, that can be performed in everyday clinical work, with a minimal surgical technique requirement, can lead to significant reductions in incidence of new ulcers.

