2. WHAT DOES THIS TRIAL ADD TO CURRENT KNOWLEDGE?

This is to our knowledge the first RCT looking at flexor tenotomies as a preventive treatment, and/or compared to conservative treatment. At the same time this is the first study looking at needle flexor tenotomies, as opposed to the classic tenotomies done by scalpel.

3. Hypothesis

We hypothesize that treating hammer, mallet and claw toe deformities in patients with type 1 and 2 diabetes, and impending ulcers (defined as nail changes, and hypercallosities at the predilection sites for ulcers associated with hammer, mallet and claw toe deformities) with needle tenotomy is a safe and effective treatment, and superior compared to offloading (conservative) treatment done by silicon spacer, insoles, felt, and/or therapeutic sandals

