4. AIM

The aim of the RCT is to evaluate the effect of needle tenotomy when treating impending ulcers associated with hammer, mallet and claw toe deformities.

The study is designed as a prospective RCT comparing needle tenotomy with conservative treatment, for patients with deformities and impending ulcers associated with the three deformities. Primary endpoint will be number of new ulcers incurred, defined as ulcers associated with hammer, mallet and claw toe deformities, placed on treated foot.

Secondary endpoints will be complications: infections (defined as ailment associated with procedure or ulcer, that is diagnosed as infection by attending health professional), transfer lesions (defined as impending ulcers or actual ulcers at anatomical sites associated with hammer, mallet and claw toes in patients with diabetes, on non-treated hammer, mallet and claw toes after surgical treatment), minor amputations (defined as amputations below ankle level), major amputations (defined as amputations at or above ankle level).

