5.2 Patients

Inclusion criteria

- Patients aged 18 years or above
- Type 1 or 2 diabetes
- Hammer, mallet or claw toe deformity
- Impending ulcer associated with above mentioned deformities
- Able to understand written and oral information
- Ability to follow planned visits and treatment
- Able to provide informed consent in Danish and/or English

Exclusion criteria

- Revascularization procedure in the affected limb planned, or undertaken within the 4 weeks prior to screening
- Hammer, mallet and claw toe that are rigid in both MTP, IP joints
- Ulcer associated with hammer, mallet and claw toe deformities
- Toe pressure < 30mmHg
- Prior major amputations on affected or ipsilateral leg
- Other corrective operation is indicated to treat patients foot deformities as deemed by investigator
- Current treatment with cytotoxic drugs or with systemically administered glucocorticoids
- Treatment of foot ulcers with growth factors, stem cells or equivalent preparations within the 8 weeks prior to screening
- Likely inability to comply with the need for planned visits because of planned activity
- Participation in another interventional clinical foot ulcer-healing trial within the 4 weeks prior to screening
- Prior enrolment in this trial
- Judgement by the investigator that the patient does not have the capacity to understand the study procedures or provide written informed consent

Discontinuation of patients

- Patient discontinues assigned treatment for any reason, while not fulfilling one of the studies accepted endpoints
- Participants who withdraw from treatment will be asked to remain in the trial for follow-up, and data will continue to be collected and analyzed.
- Patient incurs a serious adverse event (SAE), defined as death or sepsis related to the study procedure

- Investigator decides to discontinue patient due to health or compliance reasons
- Patient misses 3 consecutive visits
- Patient misses 5 or more visits during the full treatment period

Patients who discontinue the study early will be invited to have a clinical visit before being discontinued.

Patients that are discontinued will revert to their normal treatment plan, and continue in their respective clinics.

Endpoints

- New ulcer incurred
 - When/if new ulcer is incurred pictures will be send to two external evaluators to be confirmed as new ulcer
- Patient reaches 12 month visit without incurring a new ulcer

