- Patient incurs minor or major amputation on either treated or nontreated limb
- Patient receives surgical intervention relevant for the study (other than planned in study)

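### Section 5.8 analyses all harms by intention to treat and plans no analysis of operated patients, so procedure-specific harms may be diluted by patients allocated to tenotomy but never operated on

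*Combined protocol and SAP*

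**What the plan says.** Section 5.8 states, without exception: "All data will be analyzed on the intention to treat basis". The outcomes listed beneath it include efficacy and harm together. Odds ratios are planned for "The incidence of secondary infection", for "Pain in treated limb, associated with tenotomy" and for transfer lesion. Unspecified comparative methods are planned for new ulcers, amputations and "Mean time (in days) to healing of incision sites".

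Section 4 says that the secondary endpoints "will be complications: infections (defined as ailment associated with procedure or ulcer, that is diagnosed as infection by attending health professional"), followed by transfer lesions and amputations. Section 3 makes safety part of the hypothesis: treating these patients "with needle tenotomy is a safe and effective treatment".

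Three further points decide who is in the denominator:

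- The visit plan (5.4) and section 5.5.1 place randomisation at the inclusion visit. Sections 5.4 and 5.5.2 place the allocated treatment at Day 0.
- Section 5.2 says: "Participants who withdraw from treatment will be asked to remain in the trial for follow-up, and data will continue to be collected and analyzed".
- No section defines a safety, operated or as-treated population, although tenotomy complications are recorded at the visits in 5.5.3 to 5.5.5.

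**The concern.** For the new-ulcer comparison, intention to treat is the right choice. Any dilution from non-receipt works against the claim of superiority.

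For harms caused by the procedure the direction reverses. A patient who is never operated on cannot have procedural pain or a puncture-site infection, but still counts in the tenotomy arm. The observed rate then falls below the risk in patients who had the procedure, which favours the safety half of the hypothesis. A clinician who asks how often the procedure causes a complication would not get that figure from the planned analysis.

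**Working it through.** **Plan's own figure.** The plan gives no complication rate and no proportion unoperated. The only calculated figure in 5.8 is the sample size: 2 × (10 × (1.9600 + 0.8416) / 4)² = 98.11, stated as 98. Dropout gives 98/0.9 = 108.9 or 99/0.9 = 110, stated as 110. That reproduces. It matters here only for the arm size. The formula yields a per-group number, but the text does not say whether 98 is per group or in total, and no allocation ratio is stated. I assume 110 in total, split equally: 55 per arm.

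**Can an allocated patient go unoperated and still be counted?** Yes. Allocation precedes surgery by a visit. Day 0 itself provides for evaluating an ulcer that has already occurred. Patients who withdraw from treatment are kept.

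**Which outcomes are exposed?**

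| Outcome in 5.8 or recorded at visits | Diluted by unoperated patients? |
|---|---|
| Pain associated with tenotomy | Yes; it can occur only after surgery |
| Other recorded tenotomy complications | Yes, if expressed per allocated patient |
| Infection | Only the procedure-related part; section 4 also counts ulcer-related infection, so comparison by arm is legitimate |
| Incision-site healing time | No; a patient without an incision cannot enter the mean |
| Transfer lesion | Not clearly; section 4 already ties it to prior surgery |
| Amputations | Intention to treat is appropriate |

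**Dilution.** Let q be the complication risk per operated patient and u the unoperated share of the tenotomy arm. The intention-to-treat risk is q(1-u). Both q and u are assumed. The upper u of 10% supposes that all of the 10% dropout in 5.8 happens before surgery, which the plan does not say.

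| q | u | Observed risk | Expected events in 55 |
|---|---|---|---|
| 5% | 0 | 5.0% | 2.75 |
| 5% | 5% | 4.75% | 2.61 |
| 5% | 10% | 4.5% | 2.48 |
| 10% | 0 | 10.0% | 5.50 |
| 10% | 10% | 9.0% | 4.95 |

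**Effect on the planned odds ratio.** Suppose a background infection risk of 5% in both arms, q = 5%, and no operated controls.

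- u = 0: (0.10/0.90) / (0.05/0.95) = 2.11
- u = 10%: (0.095/0.905) / (0.05/0.95) = 1.99

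**No events observed.** The exact two-sided 95% upper limit is 1 - 0.025^(1/n).

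- n = 55 allocated: 6.5%
- n = 49 operated (6 of 55 unoperated, u about 11%): 7.3%

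**Full adherence.** Even at u = 0, tenotomy pain cannot occur in an unoperated control. The control cell is then zero by construction and the planned odds ratio is infinite or undefined. The informative summary is the risk among operated patients, which the plan does not specify.

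**The case against.** Intention to treat for harms is a valid comparison of two treatment strategies, and randomisation protects it. The documents do not say that any patient will go unoperated. The effect is also small: at q = 5% and u = 10%, 2.75 expected events become 2.48, well inside sampling error. Complications are recorded at visits, so the trial team could report a rate among operated patients anyway. All of this stands. It limits the point to a missing analysis. It does not remove the point, because an analysis left unplanned allows the denominator for the safety statement to be chosen after the results are known.

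A reader might go further and infer that complications in operated controls are charged to the control arm. If a share c of controls were operated on with events still recorded, the factor would be (1-u-c). At u = c = 10% and q = 5%, the result is 4.5% versus 0.5%, a difference of 4.0 points in place of 5.0. The documents do not support this reading. The section headed 7.3 offers controls tenotomy only once an ulcer has occurred. A new ulcer is an endpoint leading to the End visit, and no visit after that is described. Section 5.2 also lists as an endpoint: "Patient receives surgical intervention relevant for the study (other than planned in study"). Its sentence on continued follow-up concerns withdrawal from treatment, not patients who have reached an endpoint. Such complications would more likely go unrecorded than be counted against controls, and the plan does not say which.

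**Conclusion.** The gap is real, modest and cheap to close. Section 5.8 applies intention to treat to procedure-specific harms and plans no analysis by treatment received. Those harms would be understated by the factor (1-u): nil at u = 0 and 10% relative at u = 10%. With no events, the upper limit moves from 6.5% to 7.3%. These figures rest on an assumed u and an assumed 55 per arm.

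A reader might infer that the plan does make tenotomy look safer than it is. That is too strong. The bias depends on patients going unoperated, and the documents give no number. Nor does it reach every harm listed: incision healing is unaffected, transfer lesion is defined by reference to surgery, and the between-arm infection comparison is legitimate. What can be said is that any dilution that does occur favours the safety hypothesis, and that the plan has no analysis to show it.

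**What to change.** In 5.8:

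1. Keep intention to treat for new ulcers, amputations and the between-arm comparison of infection.
2. Add a descriptive analysis of procedure-related complications (tenotomy pain, procedure-related infection, other recorded tenotomy complications). The denominator is the patients who actually received the study needle tenotomy, with exact 95% limits. Label it non-randomised, show it beside the intention-to-treat figures, and base the safety statement on it.
3. Report any tenotomy in a control patient separately. Do not pool it: under 7.3 these patients have an ulcer, which is an exclusion criterion at entry, so their risk need not match that of preventive tenotomy.
4. State whether complications after a post-endpoint tenotomy are collected and, if so, how they are attributed.

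The cost is a short paragraph in 5.8 and one extra table. Section 4 defines infection as related to either procedure or ulcer, so the data form must record which applies if it does not already. Following complications beyond the End visit would be extra work, but item 4 asks only that the plan say whether this is done. The downsides are a non-randomised table that needs careful labelling and, if some patients go unoperated, slightly less favourable harm figures.

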5.5.5 Follow up

The following is a specification follow up visits. Performed at 3, 6 and 12 months post day 0 visit

- Foot examination
 - Inspection of pressure point, and deformities
 - o Pulses
 - o Deformities
 - o New Ulcers
- Changes in medicine/new ailments

- o Changes to the patient's medicine, and/or new diagnosis are registered
- Standard care & offloading
 - See section 5.3.2
- Impending ulcer
 - Has impending ulcer progressed to active ulcer
- Ulcer evaluation (if relevant)
 - Assessment of ulcer surroundings
 - Assessment of infection
 - Assessment of healing
 - Ulcer photo
 - o Measurement of longest length, width and depth in mm
 - Measurement of area in mm³(length*width*depth)
 - Assessment of incision site (where applicable)
 - Measurement of length, width and depth of ulcer(s) after debridement
 - o Categorizing by Texas Grading System
 - Footwear assessment
 - \circ $\;$ Footwear and/or current offloading is evaluated
 - Complications
 - Complications associated with tenotomy is registered (if relevant)
 - o SAE is registered (if relevant

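### The odds ratios for tenotomy-related pain and transfer lesion have a control count of zero by definition, so new impending ulcers on other toes, and pain, have no usable comparison with offloading alone

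*Combined protocol and SAP*

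**What the plan says.** Section 5.8 sets the intention-to-treat basis for all data and names two groups of outcomes. The first, for a comparative analysis of unspecified type, includes "Mean time (in days) to healing of incision sites". The second is introduced by "Odds-ratio will be applied to" and contains secondary infection, "Pain in treated limb, associated with tenotomy" and transfer lesion. Section 5.8 does not say which groups enter the odds ratio, gives no method for a zero cell, and does not restrict any of these outcomes to the tenotomy arm.

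Section 4 defines a transfer lesion as an impending or actual ulcer at the relevant sites, "on non-treated hammer, mallet and claw toes after surgical treatment". It defines the primary endpoint through "ulcers associated with hammer, mallet and claw toe deformities, placed on treated foot". Pain is not among the section 4 endpoints.

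Under sections 5.1 and 5.3, controls receive offloading without study surgery. Section 7.3 says controls may be offered tenotomy once an ulcer has occurred.

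The follow-up visit list (section 5.5.5) includes "Inspection of pressure point, and deformities", "Has impending ulcer progressed to active ulcer" and "Complications associated with tenotomy is registered (if relevant". The lists for days 7 and 14 (5.5.3) and the end visit (5.5.4) carry the same three items.

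**The concern.** An odds ratio compares the odds of one event in two groups that could both have it. Here the event definition contains the treatment: a lesion must follow surgery, and the pain must be linked to tenotomy. A control treated as allocated satisfies neither condition, whatever happens to that patient's other toes or limb.

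Section 3 hypothesises that needle tenotomy is safe as well as effective, and section 4 lists transfer lesions as a secondary complication. Section 3 defines impending ulcers as nail changes and hypercallosities at the sites in question. These can also appear on other toes under offloading alone, and limb pain can too. Without a control count, the planned odds ratios cannot separate an effect of tenotomy from this background.

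**Working it through.** **1. The definitions side by side**

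| Outcome in 5.8 | Condition for an event | Possible in a control treated as allocated? |
|---|---|---|
| Secondary infection | Related to the procedure or to an ulcer (section 4) | Yes |
| Transfer lesion | Follows surgical treatment (section 4) | No |
| Pain in treated limb | Linked to tenotomy (5.8) | No |
| Incision-site healing time | An incision site exists | No |

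Infection is therefore not part of this point.

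**2. The odds ratio.** With a events among n tenotomy patients and 0 among m controls, OR = a·m / ((n − a)·0). This is infinite for a ≥ 1 and undefined (0/0) for a = 0.

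**3. What is recorded in both arms**

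- *Actual ulcers:* new ulcers are looked for at every visit from day 0. At days 7 and 14 and at the end visit they are specified as those not linked to registered impending ulcers.
- *New impending ulcers:* anatomical placement is listed at inclusion and day 0 only (5.5.1, 5.5.2). From day 7 the item asks only about progression. Pressure points are inspected, but no item turns a new callus or nail change into an outcome.
- *Pain:* the only listed pain entry is in the baseline neuropathy history (5.5.1). The later complications item covers tenotomy only. The item on medicine changes and new diagnoses applies to both arms but is not a pain or callus record.

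**4. Illustration of size.** The documents give no event rate and no test for these outcomes. The assumptions are a two-sided Fisher test at 5%, 1:1 arms, every tenotomy patient at risk, and the same true lesion risk r in both arms. This concerns lesions only, because tenotomy-related pain has no control risk to equate.

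Arm sizes come from 5.8. The standard two-means formula gives 2 × (10 × (1.960 + 0.842)/4)² = 98.1, which matches the stated 98 (as printed, with σ on the first z only, it gives 52.2). For 10% dropout, 98/0.9 = 109 and 99/0.9 = 110, against the stated 110. Taking 98 and 110 as totals, as the plan does, gives 49 or 55 per arm. Whether the formula's result should be read as a per-arm size is a separate matter.

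For k v 0 with n per arm, Fisher p = 2·C(n,k)/C(2n,k):

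- n = 49: k = 5 gives 0.056; k = 6 gives 0.027.
- n = 55: k = 5 gives 0.057; k = 6 gives 0.027.

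Six events against none is thus the smallest significant result. The chance of it is P(X ≥ 6), with X ~ Bin(n, r):

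| True risk in both arms | n = 49 | n = 55 | Same lesions counted in both arms (49 / 55) |
|---|---|---|---|
| 5% | 3.5% | 5.6% | 0.7% / 0.9% |
| 10% | 36.5% | 47.6% | 1.7% / 2.0% |

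If only 40, 28, 20 or 15 of the 55 tenotomy patients keep an untreated deformed toe, the 10% case falls to 20.6%, 5.5%, 1.1% or 0.2%.

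Without any test the estimate is still unusable. At 55 per arm, 3 v 0 gives an infinite odds ratio with an exact 95% interval of 0.42 to infinity. At an assumed 3% risk, the chance of no tenotomy-arm event, and so no odds ratio, is 0.97⁵⁵ = 19% or 0.97⁴⁹ = 22%.

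**The case against.** **The control zero is not absolute.** Section 5.2 lists relevant off-plan surgery as an endpoint, returns discontinued patients to normal care and asks those who withdraw from treatment to stay in follow-up. Section 7.3 says tenotomy is already used in clinics. A control could therefore have surgery and then an event. This stands, but such events would be rare, would occur only in controls who had surgery, and would not restore a comparison with offloading alone.

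**The plan records more in controls than the odds-ratio wording suggests.** A reader might infer that lesions on other toes are not compared at all. The documents do not support that: actual ulcers on the treated foot are compared through the primary endpoint, and ulcers unrelated to registered impending ulcers are listed in both arms. New diagnoses and medicine changes are also registered in both arms. Section 5.5 refers to operating procedures that are not in the document, so the statement about recording is about this protocol, not the case report forms.

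**The illustration is hypothetical.** A reader might infer that the trial has a 37-48% chance of a false harm finding. The documents do not support that either. They give no event rate and plan no test, and section 5.3.1 may mean that most deformed toes are treated, leaving few at risk. At 5% risk the figures are near the nominal 5%. Blocks of five (5.6) also make 1:1 arms an assumption.

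**The pain item may mean procedural tolerability.** If so, descriptive reporting is enough, which supports removing the odds ratio.

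**Conclusion.** The point holds in limited form. Two of the three planned odds ratios, and the comparative analysis of incision-site healing, cannot work as worded, because controls treated as allocated have no possible event or value. This follows from the definitions and needs no assumption about rates or sample size. It rests on reading the odds ratio as tenotomy against conservative treatment by allocation, the only comparison that the plan describes.

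What is lost is a comparison of new impending ulcers on other toes, and of pain. The numerical illustration shows how a fixed zero could mislead if someone tested it; it does not estimate an error rate for this trial. The primary endpoint, the sample size, the infection odds ratio and the amputation outcomes are not affected. The plan should be changed, but the trial's main question does not depend on it.

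**What to change.** **Minimum (text only).** In 5.8, drop the odds ratios for tenotomy-related pain and transfer lesion, and the comparative analysis of incision-site healing. Report all three descriptively in the tenotomy arm.

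**Preferred (in addition).**

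- Define the lesion outcome without reference to surgery: a new impending or actual ulcer after day 0 on a hammer, mallet or claw toe that is not an index toe. Register index toes before randomisation, and state whether one or both feet count.
- Record this outcome with its location in both arms at the existing visits, and report how many patients per arm have a non-index deformed toe.
- Compare it by allocated group with an exact 95% interval.

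A rate ratio is optional. Under a constant hazard with follow-up ending at the ulcer, the planned 10% and 6% incidences give mean follow-up of 11.39 and 11.64 months (12 × p / (−ln(1 − p))), a difference of about 2%. Any-cause pain in the study limb may be added as a supportive comparison.

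**Cost.** One baseline item, one short item at existing visits and a second if pain is added; no extra visits. The recording has to be in place before follow-up starts, because control events not recorded may not be recoverable. No blinding of visit staff is described, so assessment of impending ulcers and pain may be influenced by knowledge of allocation; the report should say so. If most deformed toes are treated, few non-index toes will be at risk and the interval will be wide.
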